C. Study Design flow. Primary care or mental health outpatient clinics agreeing to participate will be randomly selected (N=80 total) and initially offered REP for six months in order to implement LG. Based on previous research and preliminary data, it is expected that after six months of REP at least two-thirds of sites will be non-responsive to REP. The primary focus of the randomized comparisons in this study are sites that are initially non-responsive to REP (k=40), defined based on our preliminary studies as <10 patients receiving LG within six months of initiating REP and that patients received <75% group sessions. (Although not part of the primary randomized comparisons, sites that are responsive at 6 Months will continue to be followed and outcomes will be assessed). The non-responsive sites will be randomized 1:1 to receive additional External Facilitation (**REP+EF**) or External plus Internal Facilitation (**REP+EF/IF**). After another six months (at Month 12), sites that are still non-responsive (based on the same criteria) will be randomized 1:1 to either continue **REP+EF** or augmentation with IF (**REP+EF/IF**). All sites are followed for a total of 24 months. Patient-level outcomes will be assessed by study staff using assessments considered part of routine clinical care (e.g., symptoms and quality of life) starting at the initiation of REP and then at 6, 12, 18, and 24 months later among a pre-selected cohort of n=20 patients per site who are identified by site providers for LG (total patients participating in the project N=k*n=800). Patients receiving Life Goals as part of their routine clinical care may opt in or out in participating in the outcomes assessment component. As with our prior implementation work (R01 MH79994), independent evaluators (study staff who are not aware of the assignment to **REP+EF** or **REP+EF/IF**) will conduct study outcomes assessments to ensure consistency of

data collected across sites and to prohibit provider/site or investigator assessment bias. Pre-identification of LG recipients also maximizes consistency of the patient population across sites (see patient criteria below).

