D. Site Organizational Randomization: The unit of randomization is the site and will be stratified using a minimization allocation method. This procedure will ensure that groups are balanced for site variables that may correlate highly with outcomes. The Month 6 randomization for REP non-responsive sites, will be stratified by state, type of practice (primary care or mental health site), and site-aggregated mean mental health related quality of life measured at Month 6. The Month 12 randomization for non-responders to **REP+EF** will be stratified by site-aggregated quality of life measured at Month 12. Based on interviews with site leaders and the literature, participating sites differ more by state and practice type than by type of network, and state and practice are correlated with mental health related quality of life and number of LG encounters.

E. Implementation Components (Table 1)

REP: All sites will receive REP (Table 1) in the first three months and will be monitored monthly up to the sixth month in the use of LG. REP includes dissemination of the LG package, training, and LG uptake monitoring for up to six months. REP includes an off-site trainer, which is neither an External nor Internal Facilitator. The following REP components were previously operationalized by study investigators (R01 MH79994):

Step 1: Dissemination of LG package, in-service, and patient selection: Each site will designate at least one provider with a mental health background (master’s in social work, nursing degree, or bachelor’s with two years’ experience in mental health psychosocial treatment) to implement LG (“LG provider”). Regional two-hour in-services will be provided by study investigators who will give an overview of LG including the evidence, and details on how to implement LG in their setting. During the in-service, the LG package will be disseminated and the REP trainer will coach the LG providers in pre-identifying a cohort of patients.

Table 1: Summary of REP, REP+EF, and REP+EF/IF Implementation and Fidelity Measures

Implementation Component	REP	REP+EF	REP+EF/IF
REP (REP)	All sites	Randomize to Non-Responding Sites	Randomize to Non-Responding Sites
Step 1: Disseminate package: LG in-service and identify appropriate patients using medical record review	√	√	√
Step 2: Train site providers in LG	√	√	√
Step 3: Monitor LG uptake via monthly reporting sheets	√	√	√
REP+External Facilitator (REP+EF)			

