Intent-to-treat. Every effort will be made to collect patient level outcomes across all 80 sites and patients (N=1600) to conduct the primary and exploratory analyses (see below). The 40 sites randomized at month 6 (total 800 patients) will be included in the intent-to-treat randomized sample. The Primary Aim analysis will compare strategies in non-responding sites (k=40) beginning with **REP+EF/IF** versus strategies beginning with **REP+EF** on longitudinal change in patient-level SF-12 mental health scores (MCS- primary outcome). This analysis is a comparison of cells A+B+C vs. D+E (Figure 2). For this analysis, the longitudinal outcome is SF-12 mental health scores measured at Months 6 (pre-randomization), 12, 18, and 24. The primary contrast is the between groups difference in change from Month 6 to Month 18. The follow-up contrast at Month 24 will also be examined in this and all subsequent analyses. Linear mixed models (LMM), also known as random effects models, fit with SAS PROC MIXED will be used to analyze the longitudinal data. LMMs use all available measurements, allowing subjects to have an unequal number of longitudinal observations and producing unbiased parameter estimates as long as unobserved values are missing at random. The analysis will fit a 3-level (repeated measures for each person clustered within site) LMM with fixed effects for the intercept, time, group, and a group-by-time interaction term, where group is an indicator of **REP+EF/IF** vs. **REP+EF**. The LMM will also include random effects for site and time, an unstructured within-person correlation structure for the residual errors, and it will adjust for the following pre-randomization measures collected through Month 6: state and type of practice (primary care- or mental health site). Model diagnostics will be used to determine the suitability of more parsimonious (e.g., autoregressive) correlation structures, and nonlinear (e.g., piecewise linear or quadratic) effects for time. LMMs similar to the above for the primary outcome will be conducted for the secondary outcomes: **REP+EF/IF** vs. **REP+EF** on change in number of LG encounters, functional impairment, and psychiatric symptoms.

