The goal of the Secondary Aim 1 analysis is to determine whether continuing **REP+EF** versus augmenting with **REP+EF/IF** leads to changes in outcomes, among sites who are non-responsive at Month 12. This analysis is a comparison of cells B vs. C (Figure 2). Both primary and secondary longitudinal outcomes above will be examined using an LMM similar to that described above, except (a) including only the subset of sites that do not respond at Month 12 to **REP+EF**, (b) using monthly longitudinal outcomes from Month 12 to Month 24, and (c) the LMM will use dummy-indicators for time (i.e., time-saturated model since there are only 3 measurement times for each longitudinal outcome).

The Secondary Aim 2 analysis will involve an analysis of implementation costs. The implementation (REP, EF, IF) costs will be summed for each site as a measure of total costs and changes in costs will also be assessed over time (6, 12, 18, 24 months). An exploratory analysis of the incremental effectiveness of IF by comparing costs from sites given **REP+EF/IF** versus those with **REP+EF** will be conducted from the site's perspective. In regression models of costs, Generalized Linear Models with log link functions will be used to correct for heteroscedasticity and reduce the impact of outliers. Effectiveness will be measured by changes in health utilities using the SF-6 (a subset of SF-12 questions) as well as the Euro-QOL 5D. Cost-effectiveness will be calculated as the ratio of incremental average site-level cost and incremental average effectiveness (change in patient-level utilities) of IF. A standard nonparametric bootstrapping approach will be used to calculate confidence intervals and cost-effectiveness acceptability curves.

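### The Month 12 re-randomisation is minimised on quality of life alone, dropping practice type and state without a stated reason, in the trial's smallest randomised comparison

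*Combined protocol and SAP*

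**What the plan says.** Section V.D (Site Organizational Randomization) gives the purpose of minimisation: "This procedure will ensure that groups are balanced for site variables that may correlate highly with outcomes". The Month 6 allocation "will be stratified by state, type of practice (primary care or mental health site), and site-aggregated mean mental health related quality of life". The Month 12 allocation of REP+EF non-responders "will be stratified by site-aggregated quality of life measured at Month 12". The next sentence says that "state and practice are correlated with mental health related quality of life and number of LG encounters".

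In section VI, the Secondary Aim 1 analysis uses the Month 12 randomisation: "This analysis is a comparison of cells B vs. C". It covers the primary and secondary outcomes, and the secondary outcomes include number of LG encounters. The model is described as similar to the primary linear mixed model, which adjusts for state and practice type. Three exceptions are listed (the subset of sites, the time window, and indicator coding of time), and none removes those covariates.

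The documents give no expected number of sites, power or balance figure for B vs C.

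**The concern.** By the section's own criterion, a site variable that correlates with outcomes should be balanced. State and practice type are named as such variables and used at Month 6, then left out at Month 12 without explanation.

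Balance achieved at Month 6 does not carry over. It equalises REP+EF against REP+EF/IF, and does not constrain how the REP+EF non-responders later divide between B and C. Balancing quality of life covers practice type only as far as the two are correlated, and LG encounters are an outcome in their own right.

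B vs C is the smallest randomised comparison in the trial, so chance imbalance is likeliest there. It is the randomised evidence on whether to add an Internal Facilitator at Month 12 or continue with External Facilitation alone.

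**Working it through.** **Number of sites (an inference).** Section VI: "The 40 sites randomized at month 6 (total 800 patients) will be included in the intent-to-treat randomized sample". Section V.C: "The non-responsive sites will be randomized 1:1 to receive additional External Facilitation" or External plus Internal Facilitation, so about 40/2 = 20 sites start REP+EF. Month 12 non-response is assumed to be 1/3, 1/2 or 2/3, giving 20/3 = 6.7, 10 and 13.3, or about 7, 10 and 13 sites. The 50% response that section IV reports after External Facilitation was added corresponds to 10.

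**Chance of a lopsided split.** The practice mix is not stated, so assume half primary care, as near as the site count allows. For k sites of which m are primary care, and an arm of n1 sites that receives x of them, P(x) = C(m,x)·C(k−m,n1−x)/C(k,n1) when allocation ignores practice type. The event counted is a gap of at least 50 percentage points between the arms. The last two columns simulate minimisation with probability 0.9 of taking the better-balancing arm and quality of life in two levels. Ranges reflect set-up details that the plan leaves open.

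| Sites (m; arms) | Exact, practice type ignored | Minimised on quality of life only | Practice type added |
|---|---|---|---|
| 7 (3; 3 vs 4) | 5/35 = 14% | 14-15% | about 2% |
| 10 (5; 5 vs 5) | 52/252 = 21% | 13-20% | about 1% |
| 13 (6; 6 vs 7) | 176/1,716 = 10% | 10-11% | under 1% |

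**Sensitivity.**
- The exact figures jump with site count because one site moves a small arm a long way: 8 sites (4 and 4) give 34/70 = 49%, and 12 sites (6 and 6) give 74/924 = 8%.
- With about 30% primary care, the exact figures at 7, 10 and 13 sites are 43%, 17% and 7%.
- If quality of life and practice type correlate at an assumed 0.5, deterministic minimisation on quality of life gives 13%, 17% and 6%: some protection, but incomplete.
- If the practice mix itself varies by chance, the figure at 7 sites with practice type added is about 5-7%.
- With a weaker allocation probability of 0.8 and both practice type and state added, it is 7-8%, 3-5% and 2%.
- For scale, a gap of 40 points or more has probability 2.6% among 40 sites split half and half without any control, against 17/35 = 49% at 7 sites and 21% at 10.

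**Cost once the model adjusts.** With ten sites split 4:1 vs 1:4, the correlation between arm and practice type is (4×4 − 1×1)/(5×5) = 0.6. The site-level variance of the adjusted B−C estimate rises by 1/(1 − 0.6²) = 1/0.64 = 1.56, so its standard error rises by √1.56 = 1.25. Intercept, arm, practice type (1) and state (2) use five site-level parameters, leaving about 10 − 5 = 5 degrees of freedom with ten sites and 7 − 5 = 2 with seven.

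**Cost of adding practice type.** At 10 sites the mean absolute difference in the two-level quality-of-life factor goes from about 0.10 to 0.13. Its level depends on how quality of life is cut, but in the set-ups tried the increase was no more than about 0.03.

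**The case against.** The strongest reply is that the analysis already deals with this. The B vs C model is modelled on the primary one, which adjusts for state and practice type, and no listed exception takes them out. This largely stands. A reader might infer that a lopsided split would shift the B vs C contrast directly and pass for, or hide, an Internal Facilitator effect. The documents do not support that. A shift of 1.2 MCS points, (0.8 − 0.2) × 2, can be produced only by assuming that practice types differ by 2 points in Month 12-24 change and by leaving the contrast unadjusted. V.D reports a correlation with quality of life, not with its change. A main-effect covariate would not absorb a difference in change by practice type, but the documents assert none. Nor is the earlier trial's 1.22 in section IV a fair yardstick: it compared REP+EF/IF with REP alone.

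Adjustment does not make balance unnecessary, however. It costs variance and leans on the model when few sites remain.

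A second reply is that few balancing factors is a defensible choice with so few sites. This has force for state, which has three levels and would give sparse margins. It has little for practice type, which has two levels and costs little balance on quality of life.

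Third, quality of life is itself a partial proxy. That also stands, to the modest extent shown in the working.

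**Conclusion.** The point holds as an unexplained inconsistency in V.D with a moderate, avoidable cost. Under the assumptions of 7, 10 or 13 sites and a half-and-half mix, a practice-type gap of at least 50 points has a chance of about 10-21%, reducible to about 2% or less. The harm is lost precision and a model-dependent estimate with few site-level degrees of freedom, rather than uncorrected confounding.

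The count of 7 to 13 sites should not be read as a figure from the plan. A risk of about 22% at 7 sites should not be quoted for a half-and-half mix either: it arises only if each site's practice type is treated as an independent coin flip, and the half-and-half figure is 14%. Only a secondary comparison is affected; the Month 6 allocation and the primary contrast are untouched. The change is worth making because it is cheap and cannot be made once the Month 12 allocation is done.

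**What to change.** In V.D, change the Month 12 sentence so that the re-randomisation is minimised on type of practice as well as Month 12 site-mean quality of life. State is optional given the few sites; if it is left out, say why. In VI, under Secondary Aim 1, state explicitly that the B vs C model adjusts for practice type and state. It would also help to give the expected number of B vs C sites.

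The cost is two or three sentences and one or two extra inputs to the minimisation, using site characteristics already held from Month 6. The statistical price is the slightly looser balance on quality of life shown in the working. At about 7 sites some coarse imbalance will remain whatever the method.

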F. Data Collection and Measures

Data for primary and secondary aims will be collected by study staff from patient surveys, organizational surveys, and provider logs. The assessment package previously developed and implemented by study investigators (R34 MH74509, R01 MH79994) was informed by the RE-AIM framework for evaluating implementation of EBPs. Key measures include patient-level outcomes, LG uptake and fidelity, organizational factors, and REP, EF, and IF activities (Table 3). Data sources include patient-level (surveys), site-level (provider surveys), and project staff logs.

Patient data: Lists of patients and contact information that were identified by the LG providers during the first 3 months of REP (pre-randomization) will be sent to study outcomes assessors who will conduct phone surveys at baseline (after the REP provider training is complete), and 6, 12, 18, and 24 months later. Patient baseline assessments will include assessments already used

in routine clinical care and will be conducted by project staff by phone after the LG provider identifies eligible patients but before the first LG sessions are implemented. Once project staff receive patient lists, they will contact patients, describe the purpose of the study, and ask if the patients would like to participate. Patients will be compensated \$10 for completing each assessment. Patient-level data will be coded with a unique identifier. There will be a crosswalk file that is password protected that is only available to be accessed by study staff that will link unique study ID with a link to the person's identity.

Table 3: Primary and Secondary Assessments – Baseline and Follow-ups

Aims	Measure	Source
1a. Primary outcomes	Health-related quality of life-SF-12 mental health score	Patient survey
1b. Secondary outcomes	Functional impairment-WHO-DAS	Patient survey
	Psychiatric symptoms-PHQ-9, GAD-7, ISS	Patient survey
	LG fidelity and uptake (# sessions, contacts)	LG provider logs, patient surveys
Secondary aims	LG implementation costs (patient, site perspective)	Patient survey, chart review, logs
	REP costs	Study staff logs
	Facilitation costs	Staff, LG provider, Facilitator logs
Covariates	Patient demographic, clinical factors, behaviors use	Patient survey, chart review, logs
	Organizational factors (OTM, ORCA, EBPAS)	Site leader, provider surveys

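### The patient surveys have two unreconciled time origins, and one of them puts the Month 6 pre-randomisation score after the Month 6 allocation

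*Combined protocol and SAP*

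**What the plan says.** The combined protocol and SAP gives the survey schedule twice.

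- **Section V.C (Study Design flow)** has patient outcomes assessed "starting at the initiation of REP and then at 6, 12, 18, and 24 months later". The same section allocates non-responsive sites after six months of REP, makes a second allocation at Month 12, and ends site follow-up at 24 months.
- **Section V.F (Patient data)** has assessors "conduct phone surveys at baseline (after the REP provider training is complete), and 6, 12, 18, and 24 months later". The patients are those "identified by the LG providers during the first 3 months of REP (pre-randomization"). The baseline call comes "after the LG provider identifies eligible patients but before the first LG sessions are implemented".

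Two other sections depend on when the Month 6 survey happens.

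- **Section V.D (Site Organizational Randomization)** balances the first allocation on, among other factors, "site-aggregated mean mental health related quality of life measured at Month 6". The second allocation is stratified by the site mean at Month 12.
- **Section VI (Analyses and Evaluation)** defines the primary longitudinal outcome as "SF-12 mental health scores measured at Months 6 (pre-randomization), 12, 18, and 24". The primary contrast is the between-group difference in change from Month 6 to Month 18.

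No section gives a survey window, requires the Month 6 survey to be finished before a site is allocated, or says how a survey completed after allocation is to be handled.

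**The concern.** Section V.F is the section from which calls would be scheduled. It counts follow-up from a baseline that comes later than REP start, whereas randomisation is counted from REP start. If staff follow V.F, the survey labelled Month 6 is taken after the site has been told its strategy and facilitation has begun.

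Three things are then at stake:

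- The starting value of the primary contrast may already contain some effect of the randomised strategy.
- The Month 6 site mean needed for minimisation may be partly or wholly missing when the site is allocated.
- The same problem recurs at Month 12, which is both the stratifier for the second allocation and the starting point of the Secondary Aim 1 analysis.

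A survey taken after allocation cannot be turned into a pre-randomisation value later, so this has to be settled before data collection reaches Month 6.

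**Working it through.** **Inputs from the documents**

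- Allocation at REP month 6 and re-allocation at month 12 (V.C; the fidelity paragraph in V.E).
- Follow-up surveys 6, 12, 18 and 24 months after the starting survey (V.C and V.F).
- Baseline at REP start (V.C), or after provider training and patient identification (V.F).
- Identification during REP months 0 to 3 (V.F). Consistently, V.E says "All sites will receive REP (Table 1) in the first three months and will be monitored monthly up to the sixth month", with the in-service and patient identification as Step 1 and provider training as Step 2.

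**Timeline.** Let b be the lag in months from REP start to the baseline survey. Each survey then falls at REP month b + {0, 6, 12, 18, 24}. Section V.C sets b = 0, and the Month 6 survey lands at 0 + 6 = 6, which is the plan's stated timing. Even then it must be completed before the site is allocated in that same month. Section V.F implies b above 0.

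| Lag b | Baseline | 6-month | 12-month | 18-month | 24-month | 6-month survey after allocation by |
|---|---|---|---|---|---|---|
| 0 | 0 | 6 | 12 | 18 | 24 | 0 months |
| 1 | 1 | 7 | 13 | 19 | 25 | 1 month |
| 1.5 | 1.5 | 7.5 | 13.5 | 19.5 | 25.5 | 1.5 months |
| 2 | 2 | 8 | 14 | 20 | 26 | 2 months |
| 3 | 3 | 9 | 15 | 21 | 27 | 3 months |

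For every b above 0, the 6-month survey follows the first allocation, the 12-month survey follows the second, and the 24-month survey passes the stated end of follow-up. Three months is not a ceiling on b. It limits when patients are identified, not when they are called.

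**Effect on the Month 6 to 18 contrast.** The documents give neither the distribution of b nor the shape of the effect over time, so these figures are illustrations under stated assumptions.

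1. *Effect starts at allocation, rises linearly, levels off at Month 12.* Share already present at the 6-month survey = b/6.
   - b = 1: 1/6 = 17%. b = 3: 3/6 = 50%.
   - b uniform on 0 to 3 (mean 1.5): 1.5/6 = 25%.
   - b uniform on 1 to 3 (mean 2): 2/6 = 33%.
2. *Same start, levels off at Month 18.* Share = b/12.
   - b = 1: 8%. b = 3: 25%.
   - Mean lag 1.5: 1.5/12 = 12.5%.
3. *Two-month start-up delay, then a linear rise from Month 8 to Month 12.* Share = max(0, b − 2)/4.
   - b uniform on 0 to 3: mean of max(0, b − 2) is 1/6, so (1/6)/4 = about 4%.
   - b uniform on 1 to 3: mean is 1/4, so (1/4)/4 = about 6%.
4. *Linear growth continuing past Month 21.* Both ends of the contrast move by b, the interval stays 12 months, and with lags up to 3 months nothing is lost.

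**The case against.** The best defence is that the intent is plain. Section VI labels the Month 6 score pre-randomisation, V.D cannot use a site mean that does not yet exist, and V.C ties the schedule to REP start. On that view V.F is loosely worded and the other three sections govern. This stands as evidence of intent. It does not remove the conflict, because V.F is explicit about where baseline sits and counts the later surveys from it, and nothing elsewhere overrides it or supplies a window.

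Four stronger readings are tempting, and the documents do not support them.

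- *Each patient runs on an individual clock.* No section says so. Completion of provider training can be read as a site-level event. The conflict does not depend on this, since training comes after REP starts and a common site lag is still a lag.
- *No patient list can exist when REP starts.* This is not shown. V.E has providers coached in pre-identifying patients at the in-service, and V.C calls the cohort pre-selected. V.F allows lists to come as late as month 3, but does not say that none comes early.
- *Randomisation would have to slip to about month 9.* The plan fixes allocation at months 6 and 12. The more likely result is an incomplete site mean, which weakens balance on one minimisation factor but does not in itself bias the comparison.
- *The contrast is always pulled towards zero, by a quarter or more.* That needs an immediate effect and an early plateau. The plan points to some delay: the internal facilitator is named only at randomisation, that person's training follows, and Life Goals itself takes four group sessions and six weekly contacts. Both arms also receive external facilitation, so only the added internal component can separate them.

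**Conclusion.** The point holds as an internal contradiction about the time origin of the surveys. As written, V.F cannot be carried out together with V.D and Section VI: whenever baseline lags REP start, and allocation takes place at months 6 and 12 as planned, the Month 6 and Month 12 scores fall due after the allocations they are meant to precede. Only the order of events is needed for that conclusion.

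The size of the harm is uncertain. Dilution of the primary contrast ranges from near zero (continued growth, or a start-up delay about as long as the lag) to an average of about a quarter to a third. The upper figures assume lags spread evenly over 0 to 3 or 1 to 3 months and an effect that builds linearly from allocation to a plateau at Month 12. They should not be read as an estimate of what the trial will lose. The matter is still worth settling firmly, because it affects both the starting value of the primary contrast and an input to each allocation.

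**What to change.** 1. State one time origin in V.C, V.F and VI. Time the follow-up surveys at Months 6, 12, 18 and 24 from the site's REP start, whatever the date of the patient's baseline survey. Describe baseline in V.C as following patient identification, to agree with V.F.
2. Give each survey a window. Require the Month 6 window to close before the site is first allocated, and the Month 12 window to close before re-randomisation.
3. Compute the site means for minimisation and stratification from surveys completed by the close of the relevant window.
4. State in Section VI that a survey completed after allocation is not used as the Month 6 pre-randomisation value.

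The cost is protocol wording and a call-scheduling rule, with no added surveys. There are two small downsides. Patients identified late have a first interval shorter than six months (about three months if baseline falls at REP month 3). Some Month 6 scores not obtained before the window closes will be missing; the planned mixed model can accommodate these under its missing-at-random assumption.
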